17. SAFETY

17.1. Safety Definitions

17.1.1. Adverse Event

An AE is any untoward medical occurrence in a participant administered a pharmaceutical investigational medicinal product and which does not necessarily have a causal relationship with this treatment. An AE can, therefore, be any unfavorable and unintended sign (including an abnormal laboratory finding), symptom, or disease temporally associated with the use of a medicinal (investigational) product, whether or not related to the medicinal (investigational) product. Only AEs that are defined as AESIs will be collected.

17.1.2. Adverse Event of Special Interest

The following AEs are considered AESIs and will be collected:

- Symptomatic hypotension: Dizziness or any other symptom or event possibly related to hypotension
- Abnormal laboratory findings of sodium, potassium, uric acid, glucose, lipids, creatinine or eGFR
- Headache
- Peripheral edema
- Any other symptom or laboratory abnormality that led to permanent discontinuation of trial medication.

17.1.3. Serious Adverse Event

An SAE is any untoward medical occurrence that at any dose; results in death, is life-threatening, requires inpatient hospitalization or prolongation of existing hospitalization, results in persistent or significant disability/incapacity, or is a congenital anomaly/birth defect. Important medical events that may not result in death, be life-threatening, or require hospitalization may be considered serious when, based upon appropriate medical judgment, they may jeopardize the patient or subject and may require medical or surgical intervention to prevent one of the outcomes listed in this definition. Hospitalization means the participant has been formally admitted to a hospital for medical reasons. It does not include a presentation at a casualty or emergency room. Hospitalization for elective treatment of a pre-existing condition that did not worsen during the study is not considered an SAE or AE. Complications that occur during hospitalization are AEs. If a complication prolongs hospitalization or otherwise meets seriousness criteria, the event is an SAE.

17.1.4. Intensity/Severity of an AESI/SAE

All AESI/SAEs will be graded as mild, moderate, or severe by the investigator based on her/his medical

judgment and the following guidance:

- **Mild:** asymptomatic or mild symptoms; clinical or diagnostic observations only; intervention not indicated.
- **Moderate:** limiting age-appropriate instrumental activities of daily living (e.g. preparing meals, shopping for groceries or clothes, using the telephone). Minimal, local or non-invasive intervention indicated.
- **Severe:** Medically significant but not immediately life-threatening; disabling; limiting self-care activities of daily living (e.g. bathing, dressing and undressing, feeding self); hospitalization or prolongation of hospitalization indicated.

17.1.5. Relationship to the Trial Medication

All AESIs/SAEs will be assessed for causal relationship to the study medication by the investigator and reported as either definitely, probably, possibly, unlikely related, or not related.

17.1.6. Serious Unexpected Suspected Adverse Reaction

A suspected unexpected serious adverse reaction (SUSAR) is a suspected adverse reaction related to an investigational medicinal product that is both unexpected and serious. An SAE will be considered unexpected if the nature, severity, or frequency of the event is not consistent with the information previously described for the trial medication in the Investigator Brochure (IB).

17.2. Safety Reporting

17.2.1. AESI/SAE Data Collection & Follow-Up Period

AESI/SAE data will be collected and followed-up from the time signed informed consent is obtained and up to the Week 8 EOT visit for the double-blind period. For participants continuing in the Open-Label Extension Period, AESIs/SAEs will be collected up to and including the Week 52 visit. Follow-up information on ongoing AESIs/SAEs obtained after the participant's respective EOT visit (as applies) will not be collected in the eCRF.

17.2.2. Trial Investigator Responsibilities in Reporting AESIs/SAEs

Regardless of the suspected causality, every AESI/SAE must be reported by the site investigators as per the local regulatory and ethical requirements. All SAEs should be reported by completing the paper (Council for International Organizations of Medical Sciences [CIOMS] or relevant form) and eCRF SAE Form. The reports should identify participants by unique identification numbers assigned to the trial participants. SAEs should be promptly reported to the concerned parties and followed-up until resolution as per the local ethical and regulatory requirements. The Investigator should supply additional information (e.g. laboratory results, specialist/hospital letters, and autopsy results, etc.) if required by the CRO. Investigators are responsible for assessing if an AE meets the criteria for reporting as serious, the intensity of the event, and the relationship of the event with the trial medication.

17.2.3. Reporting of AESIs & SAEs

At each trial scheduled visit and unscheduled visits during the trial, site staff will ask participants about the incidence of any AESIs or SAEs since the previous visit. Other AEs will not be recorded since these drugs are well-known and established with widespread use. Site staff may also become aware of the incidence of AEs during a phone call with participants. All SAEs that site staff becomes aware of from the time informed consent is obtained until 30 days after discontinuation of the trial medication must be recorded. The following information will be collected for each AESI and SAE: event name, date of onset, severity, a possible cause of the event, relationship to trial medication, action taken regarding the trial medication, treatment given to manage the event (if applicable), the outcome of event, and date of resolution (if applicable).

An increase in the severity of a previously reported AESI or SAE during the trial will be reported as a new AESI or SAE with higher severity. A decrease in the severity of a previously reported AESI or SAE during the trial, will not require changes to the reported severity. Worsening of a condition, recurrent episodes, and further complications if any are to be reported as a follow-up of the original event.

All SAEs will be reported by the site staff to the sponsor via the eCRF within 24-hours of first becoming aware of the event. Additional information will be collected including, seriousness criteria, hospitalization date and discharge (if applicable), and procedures performed (if applicable).

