9.2.2. Secondary

- Percentage of participants with an SAE from randomization to Week 4.
- Percentage of participants with symptomatic hypotension from randomization to Week 4.
- Percentage of participants with serum sodium concentration below 135 mmol/l at Week 4.
- Percentage of participants with serum sodium concentration above 145 mmol/l at Week 4.
- Percentage of participants with serum potassium concentration below 3.5 mmol/l at Week 4.
- Percentage of participants with serum potassium concentration above 5.5 mmol/l at Week 4.
- Percentage of participants with serum sodium <135mmol/l or >145 mmol/l, and/or serum potassium <3.5 mmol/l or >5.5mmol/l at week 4.
- Percentage of participants with eGFR drop of over 30% from randomization to Week 4.
- Percentage of participants with postural hypotension at Week 4
- Percentage of participants with postural hypertension at Week 4

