3.11.1.2 Adverse Event Summaries

For the summary of safety parameters, AEs will be classified according to the treatment period and treatment received as of the start date of the AE (Section 3.5.3). If an AE is ongoing at the time of randomization, it will be allocated to the Period 1 treatment. If a treatment ongoing at randomization worsens following randomization, the AE worsening will be allocated to the Period 2 treatment.

AESIs and SAEs will be classified according to the MedDRA (Medical Dictionary for Regulatory) system (version 24.0, March 2021) and summarized by system organ class and preferred term.

Treatment periods for AE summary include: Period 1/Run-in Period, Period 2, Period 3 and Post-Randomization (Periods 2 and 3). The total number of events and incidence of participants experiencing AESIs will be tabulated by treatment group and overall for the specified study periods.

For each period, any AESI or SAEs that emerges or worsens during the period of interest will be summarized:

- Adverse Events of Special Interest,
- Serious AE,
- Related AESIs – defined as those judged by the investigator to be ‘possibly’, ‘probably’ or ‘definitely’ related
- Related SAEs – defined as those judged by the investigator to be ‘possibly’, ‘probably’ or ‘definitely’ related
- AE leading to trial medication discontinuation
- AE leading to trial discontinuation – defined as a request by the participant to withdraw from future follow-up visits

Note: Clinical laboratory values noted as out of range at Week 4 that were also noted as out of range at screening will not be considered emergent AESI.

Summaries of AESI and SAEs occurring during the Randomized Period will include risk differences with 95% CI, computed using the Newcombe hybrid score method (with continuity correction; DOI: 10.1177/0962280211415469), to evaluate each GMRx2 dose levels against Placebo. Risk differences will also be computed between GMRx2 dose levels for exploratory comparison. System organ classes and preferred terms with events occurring in at least 1% of the sample will be included.

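### Protocol 17.2.3 is inconsistent on worsened events, and a symptom that recurs after randomization can be dated to the placebo run-in and missed in the randomized safety comparison

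*Protocol*

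**What the plan says.** **Site reporting (Protocol 17.2.3).** An increase in the severity of an event already on record "will be reported as a new AESI or SAE with higher severity". After one sentence on decreases in severity, the paragraph continues: "Worsening of a condition, recurrent episodes, and further complications if any are to be reported as a follow-up of the original event". The data listed for each event begin with "event name, date of onset, severity, a possible cause of the event" and end with a resolution date. No date for a later episode is listed.

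**Collection window (Protocol 17.2.1).** "AESI/SAE data will be collected and followed-up from the time signed informed consent is obtained", so the 2-week placebo run-in is included.

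**Allocation to period (SAP 3.11.1.2).** "AEs will be classified according to the treatment period and treatment received as of the start date of the AE". An event still present at randomization belongs to Period 1. If it then worsens, "the AE worsening will be allocated to the Period 2 treatment". (The sentence speaks of a treatment that worsens; an event is evidently meant.) The period summaries cover events that emerge or worsen in the period. Recurrence is not mentioned.

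**Outcomes that use these records.** These are the AESI and SAE risk differences for the randomized period (SAP 3.11.1.2) and a secondary safety outcome in Protocol 9.2.2: "Percentage of participants with symptomatic hypotension from randomization to Week 4".

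**The concern.** A participant has a day of dizziness in run-in, which resolves, and becomes dizzy again at the same grade on randomized treatment. Under 17.2.3 the second episode is a follow-up of the run-in event. If the record keeps its run-in onset date, the SAP's start-date rule places it in Period 1, on placebo. Nothing in the SAP brings it back, because its worsening rule concerns what was ongoing at randomization and this event was not.

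Symptoms such as dizziness and edema can come and go, and Protocol 5.7 itself expects that dizziness and hypotension may rise with GMRx2. Run-in episodes should be balanced across arms by randomization, but drug-provoked recurrences would not be. The records most likely to be lost are therefore the ones the comparison is meant to detect. Only AESIs and SAEs are recorded, so there is no wider adverse-event dataset from which to recover them. Sites that differ in how they read the two sentences on worsening may also count the same case differently.

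**Working it through.** The plan gives no figure to reproduce. The check is a reading of the rules case by case, then a rough scale.

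**1. Case by case, for an event first recorded in run-in**

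| What happens after randomization | Protocol 17.2.3 | SAP 3.11.1.2 | Result |
|---|---|---|---|
| Ongoing event rises in grade | New record (severity sentence) or follow-up (worsening sentence) | Worsening goes to Period 2 | Handled if a new record is made |
| Ongoing event worsens within its grade | Follow-up | Worsening goes to Period 2 | Intent is clear, but no listed field dates the worsening |
| Resolved event returns at a higher grade | New record (severity sentence) or follow-up (recurrence) | Start date of the record | Period 2 if a new record is made |
| Resolved event returns at the same or a lower grade | Follow-up only | No rule; start date applies | Can fall in Period 1 |

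The last row is the firm gap. It does not depend on how the two sentences on worsening are reconciled.

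**2. Number affected**

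Inputs: 295 randomized (SAP 2.6.1) at 2:2:1 (SAP 2.3.2), so an expected 295 × 2/5 = 118 per GMRx2 arm. The documents give neither a run-in symptom rate r nor a recurrence probability c. As assumptions:
- r = 2.8%, borrowed from the usual-care arm of the open-label triple-pill trial in Protocol 5.4 (dizziness, presyncope or syncope);
- c = 20% to 50%.

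Affected per arm = 118 × r × c:
- c = 20%: 118 × 0.028 × 0.20 = 0.66
- c = 50%: 118 × 0.028 × 0.50 = 1.65

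That is about 1 to 2 participants, before removing those whose grade rose and who would have a new record.

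**3. Direction and size of bias**

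With r equal across arms, the risk difference loses r × (c_active − c_placebo). It is unchanged if recurrence is equally likely in both arms, and shrinks if the drug provokes recurrence. At the extreme of c_active = 50% and c_placebo = 0, the loss is 0.028 × 0.50 = 1.4 percentage points. Alternatively, if the same share q of all cases is misfiled in each arm, the difference is multiplied by (1 − q).

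**4. Effect on an interval**

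This uses the SAP's Newcombe method with continuity correction, at the planned 100 vs 50 (SAP 2.5), with event counts assumed for illustration:

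| Active cases moved | Starting from 15/100 vs 1/50: difference (95% CI), points | Starting from 12/100 vs 1/50: difference (95% CI), points |
|---|---|---|
| 0 | 13.0 (1.3 to 22.1) | 10.0 (−1.4 to 18.6) |
| 1 | 12.0 (0.4 to 20.9) | 9.0 (−2.2 to 17.4) |
| 2 | 11.0 (−0.5 to 19.8) | 8.0 (−3.1 to 16.3) |

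One or two records change whether the interval excludes zero only when it is already near that boundary.

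**The case against.** The paragraph can be read coherently. Severity is a graded term (Protocol 17.1.4), so a rise in grade makes a new record, while worsening within a grade, recurrence and complications are follow-up. On that reading there is little contradiction, and the SAP already sends worsening to Period 2. This largely stands for events that rise in grade. However, the protocol does not draw the distinction for sites, and the reading leaves same-grade recurrence where it was.

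The step from follow-up to a run-in date is also an inference. No text says that a follow-up keeps the original onset date. Sites ask at each visit about events since the last one, and the symptomatic-hypotension outcome is worded by when it occurs, not by the date of a first record. This stands too: the records can be misdated, but it is not shown that they will be.

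Two stronger readings are tempting, and the documents support neither.
- A reader might infer that anyone with a run-in episode cannot register a later case of that symptom. A higher-grade recurrence qualifies as a new event, and the SAP assigns worsening of an ongoing event to Period 2.
- A reader might infer a large loss. Assuming 5-15% with run-in symptoms and 20-50% recurrence gives 118 × 0.05 × 0.20 = 1.2 up to 118 × 0.15 × 0.50 = 8.9 participants per arm. Neither rate is in the documents. Such a range would pool several symptoms, including headache, which is an AESI in Protocol 17.1.2 but absent from the SAP list in 3.11.1.1. It should not be set against the 5.2% vs 2.8% dizziness result in Protocol 5.4, which comes from an open-label usual-care comparison with a 6-month primary outcome.

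**Conclusion.** The point holds in a limited form. Protocol 17.2.3 is inconsistent on worsening. Together with start-date allocation in the SAP, it allows a same- or lower-grade recurrence of a resolved run-in symptom to be counted in the placebo run-in. The Period 2 AESI risk differences are exposed, and the symptomatic-hypotension outcome possibly so. Any resulting bias is toward no difference, provided that active treatment provokes more recurrences than placebo or that a similar share of cases is misfiled in each arm.

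The number affected is unknown and probably small. The estimate of about 1 to 2 of 118 per GMRx2 arm rests wholly on the assumed rates and on follow-ups keeping the original onset date. Tolerating the run-in is an entry criterion (Protocol 8.2.1), which may reduce it further. Efficacy and the Week 4 laboratory and orthostatic outcomes do not depend on event dates. The primary safety outcome, discontinuation due to an adverse event, is less exposed because action taken on trial medication is recorded separately. The matter is worth correcting because the remedy is cheap and the direction of error is the unfavourable one for a safety analysis.

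**What to change.** 1. **SAP 3.11.1.2.** State that any worsening, or any recurrence after resolution, whose episode begins after randomization counts as a Period 2 event, whether the site filed it as a new event or as a follow-up. Use the Period 2 boundary in SAP 3.5.3 so that no second definition is introduced. Correct the sentence that refers to a treatment worsening.
2. **Blinded review before lock.** SAP 3.9.3 already plans a blind meeting for protocol deviations. Add a check of every follow-up entry attached to a run-in AESI or SAE, query missing episode dates, and assign the period before unblinding. Report how many episodes could not be dated.
3. **Protocol 17.2.3.** Reconcile the two sentences so that worsening, and recurrence after resolution, each get their own record and onset date. All 295 participants are already randomized, so this helps only remaining or open-label data collection. Steps 1 and 2 protect the randomized comparison.

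The cost is a short SAP addition, a few data queries and a slightly higher reported AESI count. Where an episode date cannot be recovered, the gap can be disclosed but not closed.

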17.2.4. Reporting of SUSARs

The Medical Monitor assigned by George Clinical Safety will assess all suspected serious adverse reactions in order to determine expectedness in accordance with the known adverse effects of each investigational drug as listed in the IB. If a suspected serious adverse reaction is determined to be unexpected i.e. a SUSAR, the CRO will report to the applicable regulatory authorities within the required timelines. Follow-up reports will be generated in accordance with applicable regulatory requirements. Reports will also be provided to the overseeing IRB/IEC and Investigators as per country requirements.

17.2.5. Reporting of Pregnancy

Any occurrence of pregnancy in a trial participant during the trial from the time to signing the informed consent until 30 days after discontinuation of the trial medication will be reported by the site staff, using a pregnancy form, to the trial sponsor within 24 hours of the site staff first becoming aware of it. Pregnancy will be followed until final resolution (i.e., delivery or early termination). Congenital abnormalities/birth defects and spontaneous miscarriages should be reported and handled as SAEs. Elective abortions without complications should not be handled as AEs.

17.2.6. Reporting of Trial Medication Use Errors or Misuse

Reports of trial medication overdose, abuse, off-label use, misuse, or any other medication error should only be reported as an SAE if they are associated with suspected adverse drug reactions. Medication error refers to any unintentional error in the prescribing, dispensing, or administration of a medicinal product while in the control of the healthcare professional or participant. All trial medication overdose, misuse and other medication errors associated with suspected adverse drug reactions should be routinely followed-up to ensure that the information is as complete as possible with regards to the symptoms, treatments, outcomes, context of occurrence (e.g., error in prescription, administration, dispensing, dosage, etc.).

18. ETHICAL & REGULATORY COMPLIANCE

This trial will be designed, conducted, analyzed, and reported in compliance with ICH-GCP and local regulatory & ethical requirements.

18.1. Ethical Approval

All participating sites will submit to relevant IRB/IEC the trial protocol, PISCF and other trial-related essential documents, as required by the IRB/IEC, for review and approval. No sites will start the trial before the written approval of the IRB/IEC.

18.2. Regulatory Approval

Where applicable, the trial protocol, PISCF, and other trial-related essential documents will be submitted to the local regulatory agency as per the applicable requirement in the country.

18.4. Protocol Amendments

Any change to the protocol will be made through a protocol amendment by the SC. The participating sites will submit the amendment to the relevant IRB/IEC, and the sponsor will submit to the regulatory agencies as per the local requirements.

18.5. Adherence to the Trial Protocol

Investigators/sites will adhere to the trial protocol, comply with the ethical and regulatory requirements for the conduct of the trial. Any deviations from the protocol must not be implemented unless such a deviation is required to prevent/eliminate immediate harm to the trial participant(s). The investigator/site will document protocol deviations along with reasons and notify them to the sponsor/CRO as per the local requirements.

19. ADMINISTRATIVE SECTION

19.1. Insurance

The sponsor provides insurance to cover medical expenses and/or pay compensation in the event of a trial-related injury or death to a trial participant and indemnify (with both legal and financial coverage) the investigator/site against claims arising from the trial, except in the case of claims that arise from malpractice and/or negligence, in compliance with local regulatory and ethical requirements.

19.2. Quality Assurance

Quality assurance will be monitored by the Sponsor, including compliance with relevant standard operating procedures, regulatory and ethical requirements; database design and data monitoring; training of all study staff on protocol and procedures; documentation of all procedures and processes; communication with stakeholders; and input by the Steering Committee.

19.3. Trial Documents Retention

All essential trial documents (as defined by ICH-GCP) will be archived and retained at the trial sites as long as to comply with the requirements of the sponsor (as specified in the agreement between the sponsor and the sites) and the national and international regulations (whichever is the longest period). At the end of such period, the investigator shall notify in writing to the sponsor of the intent to destroy all such documents. If the site investigator is unable to archive or cannot guarantee the archival requirements for some or all the documents, arrangements must be made between the investigator and the sponsor to store documents outside the site, in such a way that they can be accessed in the event of a regulatory inspection. These documents should not be destroyed without prior written approval from the sponsor. In the case of investigator wanting to assign the trial records to another party, or move them to another location, the sponsor must be notified in advance.

For sites using an electronic system to store trial participants medical records and it cannot be confirmed that the electronic system is validated (as per 21 Code of Federal Regulations Part 11 or equivalent standard) or the sponsor representatives or the regulatory inspectors cannot be provided access to the electronic system the site will be requested to print the source documents needed for verification. Such printed copies should be numbered, stapled, and should be certified by the site investigator that they are exact copies with the same information as in the original source record.

